Posner and Plum in 1960 first incidentally observed that there is a considerable increase in cerebral blood flow after intravenous administration of acetazolamide during an investigation of the effects of acetazolamide in hepatic encephalopathy⁹. Acetazolamide is a reversible carbonic anhydrase inhibitor which prevents conversion of carbon dioxide to water and carbonic acid, resulting in an increased concentration of arterial carbon dioxide. Regulation of cerebral circulation is partly mediated by carbon dioxide which serves as a potent vasodilator resulting in increased cerebral blood flow. Under normal physiological conditions administration of acetazolamide can result in further dilation of the cerebral arterioles, therefore increasing cerebral blood flow¹⁰. Several studies have documented this phenomenon both in normal subjects and in patients with varying degrees of vascular pathology including subarachnoid hemorrhage and vascular insufficiency or occlusion^{1,2,10-14}. However, if cerebral perfusion has been reduced due to vasospasm, the cerebral arterioles correlating to the diseased territory have already lost their ability to dilate and will not have the expected increase in cerebral blood flow as a direct response to acetazolamide administration. Simply put acetazolamide should have no additional effect on cerebral blood flow in an area where

vasoregulatory responses are impaired. In addition, acetazolamide has been reported to have been injected intravenously with no serious complications in prior CBF studies in normal subjects and in patients with vascular pathology¹⁴.

Based on the principles of autoregulation, cerebral blood flow will not decrease until the compensatory capacity of the cerebral vasculature has been exhausted. So ideally, there is a window of opportunity for therapeutic intervention between reduction in cerebral perfusion pressure and ischemic neurological symptoms due to reduced cerebral blood flow. **We hypothesize that using CBCTP combined with an acetazolamide challenge would be able to identify abnormalities in the cerebrovascular autoregulation prior to reductions in cerebral blood flow and therefore prior to ischemic insult.** Several studies have already demonstrated a significant increase in cerebral blood flow in response to intravenous injection of acetazolamide but its application to patients with subarachnoid hemorrhage at risk of development of vasospasm has been limited^{9,10,12,15,16}.

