With our initial 10 patients we are able to report that in all 10 patients the images were successfully required. We then performed an analysis of the 20 total cerebral hemispheres (right and left). Nineteen of 20 hemispheres demonstrated a significant change in CBF perfusion in response to Diamox ($p<0.05$). Six hemispheres demonstrated a 30% change in CBF and 12 had a 15% change. In 9 hemispheres there was the expected increase in CBF in response to Diamox. In 10 hemispheres there was a decrease in CBF. There was no statistical difference in the percent change between left and right hemispheres which would correlate with the global vasodilatory effects of Diamox. Symptomatic vasospasm then only developed in 2 of our patients. In one of these patients there was a pathological decrease in CBF in response to Diamox while the other had an appropriate increase in CBF. The goal of the analysis in this extension of the study is to better understand the changes in CBF in patients that go on to develop symptomatic or clinical vasospasm based on a change in neurological exam. Unfortunately, in our first phase of the pilot study only 2 patients developed symptomatic vasospasm. The reason we are requesting an extension to 30 patients is so we can capture a

larger number of patients with symptomatic vasospasm. Then we can assess our statistical analysis to see if we can consistently see a significant lack of response (either <30% increase in CBF or a decrease in CBF) to Diamox. With only 2 patients in our initial cohort developing symptomatic vasospasm it is impossible to make a more robust statistical proposal and that is why we are submitting a request to study more cases.

As discussed before, in this study design there is no need for a control group. We are comparing our CBCT information to the conventional method which is the clinical neurological exam change which indicates clinical or symptomatic vasospasm. The data that will be statistically compared is the pre-diamox perfusion in comparison to the post-diamox perfusion. A statistically significant change increase in CBF represents an appropriate response to Diamox. Lack of change in CBF or decrease in CBF could be suggestive of potential for developing vasospasm. More data with patients who develop clinical vasospasm is needed in order to correlate these changes with this subset of patients.

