The statistics that will be performed on the data maps are outlined in the images below. Using the perfusion map values, we will calculate relative percent change or improvement factor which is detailed in the slides below. When we say the results were reproducible it means that we were able to detect a change in perfusion in response to Diamox and that the maps were of good enough quality to be diagnostic. I have included examples below.

The statistical analysis on the relative percent change in CBF was a standard basic paired t-test. This test was performed in an identical manner for each hemisphere for each perfusion parameter map. For a given hemisphere and map test here were 40 slices of the image above the orbital line, a mean measurement was made for each slice location of the hemisphere. Thus, for pre and post Diamox we obtained 40 paired samples. From these paired samples (paired meaning they shared the same slice location pre and post Diamox) the paired-test was performed by taking the difference between all of the pre and post paired samples to obtain a set of 40 differences. From these 40 difference values one can get a mean and standard deviation to obtain the T statistic where a corresponding p-value can then be calculated. For our data set, we are selecting p-value of <0.05 as significant. We do not plan to use this data for a power analysis. Reproducibility has been established, but we are now aiming to draw correlations between patients with vasospasm and their CBF response to Diamox and that is the main aim of this expanded portion of the study.

References

3. Lee, K., et al. "Triple-H' Therapy for Cerebral Vasospasm Following Subarachnoid Hemorrhage." *Neurocritical Care*, vol. 4, no. 1, 2006, pp. 68-76.

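### The pilot's 9 rises and 10 falls in CBF give no evidence of a net rise after acetazolamide, and the visible plan cannot tell a flat or falling CBF from measurement error

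*Combined protocol and SAP*

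**What the plan says.** Background and Significance sets the expected direction: "Several studies have already demonstrated a significant increase in cerebral blood flow in response to intravenous injection of acetazolamide". It adds that territories already affected by vasospasm should not show this rise.

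Under IRB Concerns, the results for the first 10 patients begin: "Nineteen of 20 hemispheres demonstrated a significant change in CBF perfusion in response to Diamox". On size: "Six hemispheres demonstrated a 30% change in CBF and 12 had a 15% change". On direction: "In 9 hemispheres there was the expected increase in CBF in response to Diamox. In 10 hemispheres there was a decrease in CBF". No mean change, SD or direction for the 15% and 30% changes is given. On outcome: "Symptomatic vasospasm then only developed in 2 of our patients". On how those two responded: "In one of these patients there was a pathological decrease in CBF in response to Diamox while the other had an appropriate increase in CBF".

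IRB Concerns also treats a significant increase as the appropriate response. It says that no change or a decrease could suggest a potential for vasospasm, and that no control group is needed. It explains that calling the results reproducible means "we were able to detect a change in perfusion in response to Diamox", with maps good enough to be diagnostic, and then treats reproducibility as settled. Each hemisphere's p-value comes from a paired t-test on 40 slices. Statistical Considerations plans to correlate percent CBF change with later vasospasm in 30 patients.

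**The concern.** A flat or falling CBF can be read as lost reactivity only if the technique tends to show a rise where reactivity is intact. The pilot does not show that. Roughly equal numbers of hemispheres went up and down, and the two vasospasm patients went one each way.

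The text nevertheless attributes all 19 changes to the drug, and its meaning of reproducible takes no account of direction. That is not agreement between repeated measurements. The visible plan has no repeat scan without the drug and no estimate of scan-to-scan error. It also has no summary of the average response in patients who stay free of vasospasm. The region-of-interest comparison with standard CTP under Data Acquisition does not test drug response. The earlier acetazolamide studies do not show that this imaging method, which FDA Considerations describes as still in experimental validation, detects the effect.

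At stake is what the 30-patient result can mean. Without an error estimate or an average response, a null or weak correlation could be written up as a statement about reactivity when it may reflect measurement error.

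**Working it through.** **Inputs (IRB Concerns).** 10 patients, 20 hemispheres; 19 significant; 9 up, 10 down; 6 at 30% and 12 at 15%; 2 patients with vasospasm.

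**The plan's own count.** 9 + 10 = 19, and 20 − 19 = 1 not significant. The count reproduces. The p-values cannot be recomputed, because no slice data are given.

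**Is there a net rise?** Exact two-sided sign test, 9 v 10: p = 1.0. Share with the expected increase: 9/20 = 45%, exact 95% CI 23% to 68%. This treats hemispheres as independent, which they are not. With 10 patients as the unit and 5 rising (assumption), the interval is 19% to 81%.

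**Does this show no effect?** No. If the true share rising were 75%, the sign test would have 47% power with 19 independent units and 24% with 10. The net mean is also open. Take 30% and 15% as exact, the 12 as including the 6, the other 7 significant changes as between 0 and 15%, and the non-significant one as 0:
- highest: (6×30 + 3×15 − 3×15 − 7×0)/20 = +9.0%
- lowest: (−6×30 − 4×15 + 2×15 + 7×0)/20 = −10.5%

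If the 12 and the 6 are separate groups, the range is −6.0% to +4.5%. Even the sign is undetermined.

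**Falls in vasospasm-free patients.** The 2 cases account for at most 2 × 2 = 4 hemispheres, so at least 10 − 4 = 6 falls lie in the other 8 patients. If each case's stated direction held in both hemispheres (assumption), the non-cases have 9 − 2 = 7 up, 10 − 2 = 8 down and 1 not significant of 16 (44% up, 95% CI 20% to 70%, hemispheres taken as independent).

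**Scan error or mixed reactivity?** Read 15% and 30% as at least that size, with the 12 including the 6. The expected count beyond c under zero-mean normal error is 20 × 2 × [1 − Φ(c/SD)]. The mixed model is half the hemispheres at mean +20% and half at −20%, SD 20% (illustrative).

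| | At least 15% | At least 30% |
|---|---|---|
| Observed | 12 | 6 |
| Zero-mean error, SD 29% | 12.1 | 6.0 |
| Mixed reactivity | 12.8 | 6.3 |

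The counts do not separate the two. If the 12 and the 6 are separate groups, zero-mean normal error fits poorly: 7.1, 5.8 and 7.1 expected against 2, 12 and 6 (chi-square 10.6).

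**Do the slice p-values rule out scan error?** If the 40 slice differences share a scan-level error with correlation ρ, t is inflated by √(1 + 40ρ/(1 − ρ)) on 39 df. With no drug effect, the chance of p < 0.05 is 5% at ρ = 0, 39% at 0.1, 75% at 0.5, 92% at 0.9 and 94% at 0.95. Values of ρ are assumptions. Shared error can produce many significant changes in both directions, but a rate near 19/20 from error alone needs a high ρ.

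**Precision of a patient-level mean in the extension.** Assume 80% of 30 stay vasospasm-free (n = 24) and SD 28.5 points. The SD is close to the hemisphere-level fit (28.9) and is carried over to patient means without direct support. The half-width is t(0.975, 23) × 28.5/√24 = 12.0 points. Power to exclude zero is 91% for a true mean rise of 20%, 69% for 15% and 38% for 10%.

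**The case against.** A reader might infer from 9 v 10 that the challenge has no net effect with this technique. The documents do not support that: the sample is small, magnitudes by direction are missing, and some patients with impaired reactivity are expected under the protocol's own hypothesis.

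In the sponsor's favour, direction is not concealed. The text gives both counts soon after the 19 of 20, calls increases expected and treats a decrease only as possibly suggestive of vasospasm. This stands. What remains is the attribution of every change to the drug and the meaning given to reproducible.

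Vasospasm-free patients are not a clean reference group either. The opening rationale ties impaired reactivity to harm only if vasospasm later occurs, so some non-cases may be impaired, and Hunt and Hess grade 1 is excluded for its lower vasospasm yield. A mean near zero in non-cases would therefore not invalidate the technique. A strict rule that their lower limit must exceed zero before any reactivity claim could suppress valid results, given 69% power at a 15% rise and 38% at 10%. This stands too.

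Non-cases already serve as the comparator in the planned correlation, and the scans do not guide care. Random scan error should then weaken the correlation; it should not create one beyond chance. That narrows the harm mainly to misreading a null or weak result.

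Finally, some statistical detail sits in figures that are not shown, so the absence of a check can be stated only for the visible text.

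**Conclusion.** The concern holds in a limited form. The pilot gives no evidence of a net rise in CBF: the expected response was seen in 45% of hemispheres, against the 95% described as changing in response to the drug. Neither absence of an effect nor scan error as its cause is demonstrated.

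That at least 6 falls occurred in vasospasm-free patients rests on the reported counts alone. The 7 v 8 split in non-cases and the 19% to 81% patient-level interval need the stated assumptions. On the visible text, a flat or falling CBF cannot be told apart from measurement error, and the plan should say so and report the average response. This is an inexpensive improvement to interpretation; it is not a reason to halt the extension.

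**What to change.** 1. Under IRB Concerns, state the pilot result as 9 of 20 hemispheres with the expected increase, 10 with a decrease and 1 not significant. Note that hemispheres are paired within 10 patients, so the 23% to 68% interval treats them as independent. Stop describing detection of a change in either direction as reproducibility or as a response to Diamox.
2. In the analysis text, before the correlation, take one percent CBF change per patient (mean of both hemispheres). Report its mean and 95% CI overall, in patients who stay free of vasospasm and in those who develop it. If the interval in vasospasm-free patients does not exclude zero, state that a rise with this technique was not demonstrated and that low or negative changes may reflect measurement error as well as lost reactivity. Use this as a limit on interpretation and still report the correlation.

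The cost is a few sentences and some extra estimates from data already being collected, with no new scans or patients. The downside is a less favourable pilot headline and possibly a weaker conclusion.

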We propose a technique using cone beam perfusion (CBCTP) with an acetazolamide challenge as a potential diagnostic tool to detect a defect in cerebral autoregulation at a time when it has not yet caused clinically apparent signs or symptoms. Acetazolamide is a carbonic anhydrase inhibitor which works to increase the arterial concentrations of carbon dioxide. Carbon dioxide is an important regulator of cerebral vasculature and serves as a potent vasodilator. Acetazolamide or vasodilatory challenge should identify subjects having an abnormal cerebrovascular reactivity capacity. More specifically, after receiving the drug there will not be the expected increase CBF in some of the subjects because they are already suffering from a disturbance in the vasculature's ability to respond to the signal for vasodilation. We ultimately believe the presence of this deficit will be helpful in identifying patients who are at risk for potential brain ischemia due to this decreased capacity to autoregulate if/when clinically significant vasospasm occurs. We predict that acetazolamide-activated regional cerebral blood flow studies will be more sensitive in the detection of mild cerebral vasospasm and will not just detect changes in cerebral blood flow as does standard perfusion imaging, but will provide information regarding changes in cerebrovascular reactivity. Under these circumstances, we would have a better predictor of those patients at risk of cerebral infarction due to delayed vasospasm. Identifying this "high-risk cohort" prior to the onset of clinically apparent symptoms would result in the institution of preventative measures such as triple H therapy³.

Background and Significance

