the utility of the research study in its application as a screening diagnostic tool to predict the subsequent occurrence of delayed vasospasm in subjects with an acute aneurysmal subarachnoid hemorrhage.

Study Methods

Inclusion criteria:

A total of 30 subjects will be enrolled in this pilot feasibility study. The following patients will be targeted for enrollment:

1. Patients with aneurysmal subarachnoid hemorrhage presenting to our institution within 24 hours of symptom onset.
2. Adults, 18 years of age or older
3. Women of childbearing potential must not be pregnant (urine pregnancy test will be required as is already done as part of standard of care)

Exclusion criteria:

Whether subjects will be invited to participate in this research will be based on the patient's medical condition and will be at the discretion of the treating physician. The following patients will be excluded automatically:

1. Contraindication to acetazolamide (i.e. sulfonamide allergy, renal or liver failure)
2. Contraindication to contrast media (Allergy or abnormal serum Cr and/or GFR based on current UW guidelines for IV contrast see Appendix A)
3. Renal insufficiency, history of renal failure or renal transplant
4. Hunt and Hess grade 1 and 5 (See Appendix B, as Grade 1 have lower yield for vasospasm and Grade 5 are by definition critically ill and unstable patients)
5. Critically ill patients who are unstable and who cannot undergo scans within the proposed timeline i.e. within 24 hours of the onset of their symptoms.

Patient identification/Recruitment/Consent:

Patients targeted for enrollment will be those referred to the Department of Neurosurgery and Neuroendovascular Surgery at University of Wisconsin meeting the inclusion criteria. Eligible candidates will be identified by the neuroendovascular or neurosurgical attending physician and will be invited to participate by a clinical care team member. If patients lack capacity to provide informed consent on their own behalf, the care team will include the next of kin in the consenting process. Subarachnoid hemorrhage patients that present with a medically unstable condition will not be considered for this study.

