Capacity for providing informed consent will be determined and documented in accordance with the institutional policy for the inclusion of patients in non-therapeutic research that presents more than minimal risk. This determination will occur by direct evaluation by the clinical care team based on interaction with the patient, existing legal documentation in the

medical record in regards to a legal guardian, healthcare power of attorney, or pre-existing disease that affects decisional capacity. The University of Wisconsin Hospitals and Clinics Clinical Policy on Informed Consent will be followed (Appendix C). Those subjects lacking formal capacity will still be included in the consenting process and will be asked to provide assent to participate. Any sign of dissent by the subject will be honored by the research team even if a surrogate has provided consent on their behalf. If a subject regains capacity prior to hospital discharge, a research team member will review the consent, research procedures that have been conducted, and will obtain informed consent for continued participation in the research. For patients that have been determined to have capacity to provide informed consent, a research team member will administer a four-question assessment to confirm understanding of the implications of participating in this research (Appendix D). If the subject or legal healthcare representative is unable to provide informed consent, then the patient will be excluded from participation.

Scan procedure:

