Acetazolamide is already an FDA-approved medication. Sullivan et al tested cerebrovascular reactivity in normal subjects in response to acetazolamide challenge and found the most common adverse reaction to be numbness and tingling which was transient over the course of several hours. Approximately half of subjects experienced headache and generalized fatigue. However, there were no serious or life-threatening reactions in any of the subjects¹⁰. Holl et al demonstrated use of intravenous acetazolamide in both normal subjects and subjects with major cerebral occlusion had no serious complications. They do report that there was a consistently produced rise in intracranial pressures (ICP) in patients with already disturbed cerebral spinal fluid (CSF) circulation, but this increase was transient and in their cohort it was symptomatic in only one patient who experienced a headache^{15,20}. In our population if there is concern for increased ICP there would be an intracranial pressure monitor that would be providing CSF diversion to reduce ICP as a standard of care placed prior to administration of the drug. Therefore, this causes essential no clinical risk to this patient population.

Privacy/Confidentiality protections and sharing of data:

Data gathered from this study will be post-processed and evaluated by the study neuroendovascular physician in accordance with the protocol outlined above. Imaging data will be stripped of all direct patient identifiers and stored on a dedicated PACS system controlled by UWHC. [name], will maintain the master list linking coded data to medical record numbers. The research workstation that will be used by analysis is password protected and uses departmental servers that are backed up by the UWHC firewall. Coded data, including images,

collected from this research will be shared with manufacturer of C-arm CBCT, Siemens Medical Solutions for further refinements in hardware and prototype software to improve imaging. No directly identifiable images or data will be disclosed outside of UWHC. All data obtained from the medical record will be stored in a HIPAA compliant manner.

Patient Follow Up:

Patients will receive follow up care by the primary treating neurosurgeon or neuroendovascular surgeon in a manner that is consistent with standard clinical care. Subjects will be inpatients and their recovery followed primarily by either the neurosurgery or neuroendovascular teams during their acute hospitalization.

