Information Collected from Medical Records

Data collected from medical records will include:

1. Age, sex, medical history, physical exam, laboratory and imaging studies
2. Hunt and Hess Grade
3. Fisher Grade
4. Intracranial pressure
5. Location of aneurysm responsible for bleeding
6. Treatment modality for aneurysm (embolization versus clipping)
7. Anesthesia record
8. Presence of vasospasm or delayed cerebral ischemia
 - a. Clinical: deterioration when other causes have been ruled out including hydrocephalus, re-bleed, or metabolic abnormalities
 - b. Radiographic: detection of new infarct on imaging not visible on the admission or immediate post-treatment scan or both

FDA Considerations:

C-arm CBCTP: Siemens C-arm CBCT software currently has 510(k) (September 2004) clearance. The innovative C-arm CBCTP software is used to consecutively perform 10 CT sweeps with one single intravenous contrast injection. We are requesting a, "non-significant risk" determination by the IRB for the use of this novel software. Note that C-arm CBCT acquisitions are routinely and frequently utilized in our clinical practice and we do not foresee any potential risks. The package of ten C-arm CBCT sweeps and the innovative data processing software SMART RECON, are not FDA approved since they are in experimental validation research stage approved by the NIH at UW. The data obtained from this study may support the application and approval of the UW software in the future. However, the hardware (Siemens angiographic machine) to obtain the C-arm CBCT perfusion data does not introduce any new potential safety risks and is equivalent to and performs in the same fashion as standard C-arm CBCT.

Data and Safety Monitoring Plan

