All researchers and research staff involved in this project have completed Human Subjects and HIPAA training and are familiar with all procedures. The PI and co-investigators will review the data collected after the initial patients have been treated and outcome data becomes available. Adverse events or problems will be reviewed by the PI and co-investigators as they occur and will be reported to the IRB by the PI in accordance with posted guidelines. The PI and the co-investigators will meet regularly to review the data, adherence to the protocol and IRB guidelines. Data and safety monitoring will occur on a continuous basis by the research staff. The study team will meet regularly to review study progress including recruitment, data collection, and they will address any concerns or challenges that may arise. If initial pilot data shows that this technique is validated a formal study will be proposed to the IRB.

Statistical Considerations

The initial pilot study was conducted as a feasibility study and no robust statistical evaluation is possible. Since we have determined that the research imaging can be achieved safely and data reproducibly collected, we now hope to amend the cohort to a total of 30 patients so that we can capture more patients with vasospasm in order to have a more robust analysis of the correlation between percent change in CBF to Diamox and the future development of cerebral vasospasm.

IRB Concerns

The gold standard for determining if a patient has vasospasm is the clinical neurological exam. There is no currently accepted radiographic method or procedure for predicting vasospasm. Therefore, when comparing this proposed CBCT approach to the competing method we would be comparing it to the clinical neurological exam. Additionally, comparisons are being made to current methods of predicting vasospasm including TCDs, multidetector CTA/CTP, and angiography.

[figure not shown]
[figure not shown]

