Appendix B:

Hunt and Hess Grading Scale

- Grade 1: Asymptomatic or mild headache
- Grade 2: Cranial nerve palsy or moderate to severe headache/nuchal rigidity
- Grade 3: Mild focal deficit, lethargy, or confusion
- Grade 4: Stupor and/or hemiparesis
- Grade 5: Deep coma, decerebrate posturing, moribund appearance

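### Does the plan need a rule for patients whose neurological exam could not have shown vasospasm?

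*Combined protocol and SAP*

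**What the plan says.** Under *IRB Concerns*, the combined protocol and SAP states that "The gold standard for determining if a patient has vasospasm is the clinical neurological exam". It describes the target group of the extension as "patients that go on to develop symptomatic or clinical vasospasm based on a change in neurological exam".

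*Exclusion criteria* item 4 removes Hunt and Hess grades 1 and 5, "as Grade 1 have lower yield for vasospasm and Grade 5 are by definition critically ill and unstable patients", so grades 2 to 4 stay eligible. Appendix B gives "Grade 4: Stupor and/or hemiparesis". Item 5 and the recruitment section also keep out unstable patients, and invitation is left to the treating physician. On consent, "Those subjects lacking formal capacity will still be included in the consenting process"; they are asked for assent, and are re-approached if they regain capacity before discharge.

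*Information Collected from Medical Records* item 8 covers vasospasm and delayed ischemia together. Item 8a is clinical deterioration with other causes ruled out. Item 8b is "detection of new infarct on imaging not visible on the admission or immediate post-treatment scan or both". The same list includes physical exam, imaging, Hunt and Hess grade and the anesthesia record. Under *Patient Follow Up*, subjects are inpatients, with "their recovery followed primarily by either the neurosurgery or neuroendovascular teams during their acute hospitalization".

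No section gives an exam schedule or a category for an uninformative exam, and none says whether 8b alone makes a case.

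**The concern.** A reference standard based on a change in the exam works only where the exam can change visibly. A stuporous patient, or one who is sedated, may have little room to show a new deficit. If such a patient is filed as free of vasospasm, a true event sits among the non-cases. Should that patient also have shown no CBF rise and later had an infarct, a correct warning from the scan would be scored as a false alarm. That would cut against the stated purpose in the introductory text, where "we would have a better predictor of those patients at risk of cerebral infarction due to delayed vasospasm".

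The reason given for excluding grade 1 ties grade to vasospasm yield, so the patients hardest to examine may not be at low risk. The correlation between vasospasm and CBF response is the main aim of the extension, and few cases are expected, so each misfiled patient would count. The pilot report does not say whether all 8 patients without symptomatic vasospasm could be examined adequately.

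**Working it through.** **1. Expected cases.** The plan gives N = 30 with no calculation, so there is no figure to reproduce. The pilot saw 2 cases in 10 patients: 20%, exact 95% interval 2.5% to 55.6%. With the 2 observed cases fixed and 20 patients to come:

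- expected: 2 + 20 × 0.20 = 6
- range: 2 + 20 × 0.025 = 2.5 to 2 + 20 × 0.556 = 13.1

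**2. Who is affected.** The documents give no grade mix. Grade 4 is stupor, hemiparesis or both, and hemiparesis alone does not prevent an exam. A stuporous patient can still worsen. The relevant exam is also the one made when delayed vasospasm would appear, not the one at enrolment within 24 hours of onset. The provision for regained capacity shows that recovery is anticipated. Any count of missed events is therefore an assumption.

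**3. Effect on sensitivity (illustration).** One of the two pilot cases had a fall in CBF. If that share holds, 3 of 6 cases are non-responders: sensitivity 50%, exact interval 11.8% to 88.2%. Let u = 1, 2 or 3 true events be misfiled (assumed).

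| | u = 1 | u = 2 | u = 3 |
|---|---|---|---|
| All non-responders, (3+u)/(6+u) | 4/7 = 57% | 5/8 = 63% | 6/9 = 67% |
| All responders, 3/(6+u) | 3/7 = 43% | 3/8 = 38% | 3/9 = 33% |

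The direction is unknown, and every value lies inside the interval.

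**4. No firm base for specificity from the pilot.** Falls occurred in 10 of 20 hemispheres, which would suggest 50%. But *IRB Concerns* counts a rise under 30%, or a fall, as lack of response. Six hemispheres had a 30% change, direction unstated, so at least 20 − 6 = 14 of 20 (70%) would be non-responders, and specificity would be at most about 30%. Under the section's other wording (no change, or a fall), 9 hemispheres rose, so 20 − 9 = 11 (55%) lack a response. Carrying hemisphere shares over to patients is a further assumption.

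**5. Wider scenarios.** Assume g = 3 to 12 grade 4 patients, vasospasm rate r = 20% or 40% in them and 20% in the rest, fraction missed f = 50% or 100%, true sensitivity 80% and specificity 70%. C is the number of true cases.

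- Missed m = g × r × f: from 3 × 0.2 × 0.5 = 0.3 to 12 × 0.4 × 1 = 4.8.
- Apparent specificity = 1 − [0.3(30 − C) + 0.8m] / [(30 − C) + m].
- Mildest, C = 6: 1 − (7.2 + 0.24)/24.3 = 69.4%.
- Most severe, C = 18 × 0.2 + 12 × 0.4 = 8.4: 1 − (6.48 + 3.84)/26.4 = 60.9%.
- Sampling error on 24 non-cases: ±1.96 × √(0.7 × 0.3/24) = ±18 points, against a shift of at most 9.
- Positive predictive value with g = 6, r = 20%, all missed (m = 1.2): 4.8/12 = 40% falls to 3.84/12 = 32%. Sampling error is ±1.96 × √(0.4 × 0.6/12) = ±28 points.
- In the most severe corner it falls from 6.72/13.2 = 51% to 2.88/13.2 = 22%. That is 29 points, about equal to its sampling error of ±1.96 × √(0.509 × 0.491/13.2) = ±27.

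**6. The two outcome texts side by side.** *IRB Concerns* speaks of an exam change. Item 8 lists new infarct as a second way in which vasospasm or delayed ischemia is recorded. Neither says that an infarct without an exam change is to be ignored, and neither says that an uninformative exam means no event. Filing such a patient as a non-case is an inference from silence.

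**The case for a change.** The strongest reply is that the exam-change wording appears twice under *IRB Concerns* and, taken literally, leaves an unassessable patient nowhere to go except among the non-cases. Item 8b is collected but is not brought into the analysis wording. TCD, CTA/CTP and angiography are named as predictors for comparison, not as a fallback outcome. With about 6 cases, losing one or two is not trivial, and a rule fixed beforehand would prevent a choice made after seeing the results.

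Part of this stands. There is no category for an uninformative exam, the status of 8b alone is unstated, and in the most severe corner of step 5 the predictive value would suffer visibly. But that corner needs 12 of 30 patients in grade 4, double the event rate in them and every one of their events missed. The documents support none of these.

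The obvious remedy, leaving unassessable patients out of the main correlation, is not clearly better. It needs a criterion for when an exam could not show a change, and that is itself a judgement. It shrinks a small sample and tilts it toward better grades. It drops the patients with infarction whom the method is meant to find. For the first 10 patients it would be applied with CBF responses and outcomes already known.

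**Conclusion.** No change to the plan is needed. The silence is real, but the documents do not show that following the plan gives a wrong result. Exam, infarct, grade and anesthesia data are all on the collection list, so the analyst can flag doubtful exams and tabulate the correlation on the exam alone and on exam or infarct. That is good reporting practice rather than a correction.

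The size is undetermined because no grade mix is given. On the assumption of 1 to 3 misfiled events among about 6 expected cases, the shift in sensitivity is 7 to 17 points in either direction, inside an interval of 12% to 88%. The study is a 30-patient feasibility pilot with no power analysis, and a formal study is to be proposed if the technique is validated. The conclusion rests on item 8b being recorded as listed and on few patients staying unexaminable through the period of delayed vasospasm. A cohort made up largely of persistently stuporous patients would make the point weightier.
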